13.6 Publications and Clinical Study Report

[figure not shown]
13.6.2 Clinical Study Report

A CSR, written in accordance with the ICH E3 Guideline, will be submitted in accordance with local regulations.

## 4 INTRODUCTION

This statistical analysis plan (SAP) is based on the most recent approved clinical study protocol (CSP), the most recent approved electronic case report form (eCRF), and the most recent approved eCRF completion guidelines.

This SAP (Methods) documents the planned final statistical analyses of efficacy and safety endpoints defined in the VX17-659-103 study protocol. [REDACTED]

The pharmacokinetic (PK) and pharmacodynamic (PD) characteristics of VX-659/TEZ/IVA in the *F508del* homozygous population also will be evaluated in the study. Selected analyses related to sweat chloride will be documented in this SAP, other PK and PD analyses will be documented separately in the clinical pharmacology analysis plan (CPAP) for the study.

The Vertex Biometrics Department will perform the statistical analysis of the efficacy and safety data; SAS (Version 9.4 or higher) will be used to generate all statistical outputs (tables, figures, listings, and datasets). The SAP will be finalized and approved prior to the final clinical database lock and treatment unblinding for the study. Any revisions to the approved SAP will be documented and approved in an amendment to the SAP prior to the clinical database lock for the final analysis. Any changes made to the SAP (Methods) after the clinical database lock has occurred will be documented in the clinical study report for this study.

## 5 STUDY OBJECTIVES

### 5.1 Primary Objective

To evaluate the efficacy of VX-659 in triple combination (TC) with tezacaftor (TEZ) and ivacaftor (IVA) in subjects with cystic fibrosis (CF) who are homozygous for the *F508del* mutation (F/F)

### 5.2 Secondary Objectives

- To evaluate the safety of VX-659 in TC with TEZ and IVA
- To evaluate the PD of VX-659 in TC with TEZ and IVA
- To evaluate the PK of VX-659, TEZ, and IVA when administered in TC

## 6 STUDY ENDPOINTS

### 6.1 Efficacy and Pharmacodynamic Endpoints

#### 6.1.1 Primary Efficacy Endpoint

Absolute change in percent predicted forced expiratory volume in 1 second (ppFEV1) from baseline at Week 4

#### 6.1.2 Secondary Efficacy and Pharmacodynamic Endpoints

The key secondary efficacy endpoints are as follows:

- Absolute change in sweat chloride (SwCl) from baseline at Week 4

[figure not shown]
- Absolute change in CF Questionnaire-Revised (CFQ-R) respiratory domain score from baseline at Week 4

## **6.2 Safety Endpoints**

Safety and tolerability will be evaluated via the following endpoints:

- Adverse events (AEs)
- Clinical laboratory values
- Standard 12-lead ECGs
- Vital signs
- Pulse oximetry

[figure not shown]

## **7 STUDY DESIGN**

### **7.1 Overall Design**

This is a Phase 3, randomized, double-blind, active-controlled, parallel-group, multicenter study. A schematic of the study design is shown in [Figure 7-1](#).

**Figure 7-1 Schematic of the Study Design**

IVA: ivacaftor; N: number of subjects; TC: triple combination; TEZ: tezacaftor

Note: The Safety Follow-up Visit is not required for subjects who complete the Week 4 Visit and have enrolled in an open-label study within 28 days after the last dose of study drug (Section 9.1.4 of the CSP).

In the TEZ/IVA Run-in Period, all subjects will receive TEZ 100 mg once daily (qd)/IVA 150 mg every 12 hours (q12h). Following completion of the TEZ/IVA Run-in Period, approximately 100 subjects will be randomized (1:1) to the TC arm or TEZ/IVA arm for the Treatment Period. The planned dosages for the Treatment Period are shown in Table 7-1.

**Table 7-1 Treatment Period Arms and Dosages**

Treatment Arm	VX-659 Dosage	TEZ Dosage	IVA Dosage
VX-659/TEZ/IVA	240 mg qd	100 mg qd	150 mg q12h
TEZ/IVA	0 mg	100 mg qd	150 mg q12h

IVA: ivacaftor; q12h: every 12 hours; qd: once daily; TC: triple combination; TEZ: tezacaftor

All visits will occur within the windows specified. Please refer to the Table 3-1 and Table 3-2 of the CSP for more details about study visits and assessments.

## 7.2 Sample Size and Power

The primary efficacy endpoint is the absolute change in ppFEV1 from baseline at Week 4. The primary null hypothesis to be tested is that the mean absolute change in ppFEV1 from baseline at Week 4 is the same for the TC and TEZ/IVA treatment groups. The null hypothesis will be tested at a 2-sided significance level of 0.05.

Assuming a within-group SD of 7 percentage points and a 5% dropout rate at Week 4, a sample size of 50 subjects in each treatment group for a total of 100 subjects will have approximately 93% power to detect a difference of 5.0 percentage points for the mean absolute change in ppFEV1 from baseline at Week 4 between the 2 treatment groups, based on a 2-sided 2-sample *t*-test at a significance level of 0.05 using the PASS software (Version 11.0).

### 7.3 Randomization

Randomization will be stratified by ppFEV1 determined during the TEZ/IVA Run-in Period (Day -14 assessment; <70 versus ≥70) and age at the Screening Visit (<18 versus ≥18 years of age). If the Day -14 ppFEV1 value is not valid or not available, the most recent available ppFEV1 value will be used for stratification.

### 7.4 Blinding and Unblinding

Refer to the CSP Section 10.7 for details.

## 8 ANALYSIS SETS

The following analysis sets are defined: All Subjects Set, Full Analysis Set, Safety Set for the Run-in Period and Safety Set for the Treatment Period.

### 8.1 All Subjects Set

The **All Subjects Set** will include all subjects who are randomized or receive at least 1 dose of study drug. This analysis set will be used for all individual subject data listings and disposition summary tables, unless otherwise specified.

### 8.2 Full Analysis Set

The **Full Analysis Set** (FAS) will be defined as all randomized subjects who carry the intended *CFTR* allele mutation and receive at least 1 dose of study drug in the Treatment Period. The FAS will be used to summarize subject demographics and baseline characteristics, and for all efficacy analyses in which subjects will be analyzed according to their randomized treatment group, unless otherwise specified.

### 8.3 Safety Set

The **Safety Set for the Run-in Period** will include all subjects who receive at least 1 dose of TEZ/IVA in the Run-in Period. This safety set will be included in individual subject data listings, unless otherwise specified.

The **Safety Set for the Treatment Period** will include all subjects who receive at least 1 dose of study drug in the Treatment Period. This safety set will be used for all safety analyses in which subjects will be analyzed according to the treatment they receive, unless otherwise specified.

## 9 STATISTICAL ANALYSIS

### 9.1 General Considerations

The Schedule of Assessments is provided in Section 3 of CSP. The precision standards for reporting safety and efficacy variables are provided in an internal Biometrics document that specifies the programming rules including the precision for derived variables.

**Continuous variables** will be summarized using the following descriptive summary statistics: the number of subjects (n), mean, SD, median, minimum value (min), and maximum value (max).

**Categorical variables** will be summarized using counts and percentages. Percentages will be presented to 1 decimal place.

**Baseline value**, unless otherwise specified, is defined as the most recent non-missing measurement (scheduled or unscheduled) collected before the first dose of study drug in the Treatment Period.

**Absolute change** from baseline will be calculated as post-baseline value – baseline value.

**Relative change** from baseline will be calculated as (post-baseline value – baseline value)/baseline value.

The **Treatment-emergent (TE) Period for the Run-in Period** will be from the first dose of study drug in the Run-in Period to (1) the first dose of study drug in the Treatment Period for subjects who complete the Run-in Period and continue to the Treatment Period, or (2) 28 days after the last dose date of study drug in the Run-in Period for subjects who do not continue to the Treatment Period (e.g., subjects who do not meet the conditions to enter the Treatment Period).

The **TE Period for the Treatment Period** will include the time from the first dose date of study drug in the Treatment Period (TC or placebo + TEZ/IVA) to 28 days after the last dose of the study drug or to the completion of study participation date, whichever occurs first.

Completion of study participation for each individual subject is defined as one of the following:

- For subjects who complete the Treatment Period and enter an open-label study within 28 days of the Week 4 Visit: the Week 4 Visit
- For subjects who complete the Treatment Period and do not enter an open-label study within 28 days of the Week 4 Visit: the Safety Follow-up Visit
- For subjects who prematurely discontinue study drug treatment during the Treatment Period but do not withdraw consent (and assent, as applicable): The ETT or Safety Follow-up Visit (if required)
- For subjects who prematurely discontinue study drug treatment during the TEZ/IVA Run-in Period but do not withdraw consent (and assent, as applicable): the ETT or Safety Follow-up Visit (if required)
- For subjects who withdraw consent or assent: date of withdrawal of consent or assent, whichever is earlier

If subjects are lost to follow-up, the date of completion of study participation will be defined as the date of the last contact.

**Unscheduled visits:** Unscheduled visit measurements will be included in analysis as follows:

- 1) In scheduled visit windows per specified visit windowing rules
- 2) In the derivation of baseline and last on-treatment measurements
- 3) In the derivation of maximum and minimum values during TE period, and maximum and minimum change from baseline values during TE period for safety analyses
- 4) In individual subject data listings as appropriate

**Visit windowing rules:** The analysis visit windows for protocol-defined visits are provided in [Appendix A](#).

**Incomplete/missing data** will not be imputed, unless specified otherwise.

**Outliers:** No formal statistical analyses will be performed to detect or remedy the presence of statistical outliers, unless specified otherwise.

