3 SCHEDULE OF ASSESSMENTS

Table 3-1 and Table 3-2 provide the schedule of assessments for the study.

All visits are to be scheduled relative to the Day 1 Visit (first dose of randomized study drug in the Treatment Period). For example, the Week 4 (± 5 days) Visit would occur after 4 weeks of study drug administration in the Treatment Period has been completed.

The Cystic Fibrosis Questionnaire–Revised (CFQ-R), [REDACTED] must be completed before any other assessment at relevant clinic visits. Remaining assessments may be performed in any order when more than 1 assessment is required at a particular time point. All assessments will be performed before study drug dosing (Section 9.6.1), unless noted otherwise.

Table 3-1 Study VX17-659-103: Screening

Event/Assessment	Screening Period (Day -56 Through Day -29)
ICF and assent (when applicable)	X
Inclusion and exclusion criteria review	X
Demographics	X
Medical history	X
CFQ-R ^a	X
CFTR genotype ^b	X
G6PD activity test	X
FSH ^c	X
Serum pregnancy test (all females of childbearing potential) ^d	X
Hematology	X
Coagulation	X
Serum chemistry	X
Urinalysis	X
Weight and height ^e	X
Ophthalmologic examination ^f	X
Complete physical examination	X
Vital signs ^g	X
Pulse oximetry ^g	X
Standard 12-lead ECG ^h	X
Spirometry ⁱ	X
Medications review ^j	X
Sweat chloride	X
AEs and SAEs	Continuous from signing of the ICF through completion of study participation

AE: adverse events; CFQ-R: CF-Questionnaire-Revised; FSH: follicle-stimulating hormone; G6PD: glucose-6-phosphate dehydrogenase; ICF: informed consent form; SAE: serious adverse event

^a The CFQ-R must be completed before the start of any other assessments scheduled for that visit.

^b *CFTR* genotyping will be performed for all subjects. If the screening *CFTR* genotype result is not received before Day -28, a previous *CFTR* genotype laboratory report may be used to establish eligibility. Subjects who have been enrolled and whose screening genotype does not confirm study eligibility must be discontinued from the study ([Section 9.9](#)).

^c FSH will be measured for any suspected postmenopausal female with at least 12 months of continuous spontaneous amenorrhea. Serum FSH levels must be in the postmenopausal range, as determined by the laboratory performing the test, to be considered postmenopausal.

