^c The Safety Follow-Up Visit is required for all subjects, unless the subject completes the Week 4 Visit and has enrolled in a separate open-label study within 28 days after the last dose of study drug (Section 9.1.4). If an ETT Visit occurs 3 weeks or later following the last dose of study drug, then the ETT Visit replaces the Safety Follow-up Visit (Section 9.1.5).

^d To enter the Treatment Period, conditions for entry (Section 9.1.3) must be satisfied.

^e The CFQ-R, [REDACTED] must be completed before any other assessments scheduled at relevant visits. Refer to Section 11.6.2 and [REDACTED]

^f Weight and height will be measured with shoes off. Following screening, height will be collected only for subjects ≤21 years of age on the date of informed consent.

^g Abbreviated and complete physical examinations are defined in Section 11.7.3. Symptom-directed physical examinations will occur at any time during the study if deemed necessary by the investigator.

^h Any female subject who does not meet the criteria for non-childbearing potential is considered to be of childbearing potential and must have pregnancy testing at the indicated time points. A definition of non-childbearing potential is provided in Section 11.7.7.1.

ⁱ All standard 12-lead ECGs will be performed after the subject has been at rest for at least 5 minutes. ECGs will be collected before dosing (as applicable).

Table 3-2 VX17-659-103: TEZ/IVA Run-in Period, Treatment Period, and Safety Follow-up Visit

Event/Assessment ^a	TEZ/IVA Run-in Period (4 Weeks)		Treatment Period (4 Weeks)			ETT Visit ^b	Safety Follow-up Visit 28 (± 7) Days After the Last Dose of Study Drug (If Applicable) ^c
	Day -28 ± 1 Day	Day -14 (Day -15 to Day -3)	Day 1 ^d	Day 15 ± 3 Days	Week 4 ± 5 Days		
Vital signs ^j	X		X	X	X	X	X
Pulse oximetry ^j	X		X	X	X	X	X
Spirometry ^k		X	X	X	X	X	X
Sweat chloride ^l		X	X	X	X	X	
Urinalysis	X		X		X	X	X
Hematology	X ^m		X ^m	X	X	X	X
Coagulation	X ^m		X ^m		X	X	X
Serum chemistry	X ^m		X ^m	X	X	X	X
PK sampling ⁿ			X		X	X	

^j Vital signs and pulse oximetry will be collected before dosing and after the subject has been at rest for at least 5 minutes.

^k Spirometry assessments must be performed before study drug dosing (see [Section 9.6.1](#)) and should be performed pre-bronchodilator ([Section 11.6.1](#)) at approximately the same time at each visit.

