9.1.2 Tezacaftor/Ivacaftor Run-in Period

The TEZ/IVA Run-in Period has a 4-week duration and is designed to establish a reliable on-treatment (TEZ/IVA) baseline for the Treatment Period. The first dose of open-label TEZ/IVA will be administered at the Day -28 Visit. The last dose of open-label TEZ/IVA will be administered in the evening on Day -1 (1 day before the Day 1 Visit).

On Day -14, spirometry and SwCl will be assessed. The Day -14 spirometry assessment will be used for stratification of randomization ([Section 9.2](#)).

Subjects who prematurely discontinue study drug treatment during the Run-in Period will not be randomized or participate in the Treatment Period ([Section 9.1.5.1](#)).

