9.6 Administration

9.6.1 Dosing

Study drug will be administered orally. All subjects will receive the same number of tablets each day to maintain the blind. Additional information is provided in the Pharmacy Manual.

Study drug will be administered with a fat-containing meal or snack, such as a standard “CF” meal or snack or a standard meal.

1. It is recommended that the dose be taken within 30 minutes of the start of the meal or snack.
2. Study drug will be administered as fixed-dose combination (FDC) tablet(s) (e.g., 2 TC or matching placebo tablets; 1 TEZ/IVA or matching placebo tablet) in the morning and as 1 IVA tablet in the evening. For each subject, doses of study drugs will be taken at approximately the same time (± 2 hours) each day.
3. The date, amount taken, and time of study drug administration, including whether food was taken with each dose, will be recorded for the 2 doses before PK sample collection and the dose received on the morning of PK sample collection (if applicable).
4. On days of scheduled visits, the morning dose of study drug (TC, TEZ/IVA, or placebo) will be administered at the site after predose assessments have been completed. A meal or snack will be provided by the site for the morning dose of TC, TEZ/IVA, or placebo.
5. If a subject’s scheduled visit is to occur in the afternoon, the following guidelines must be used:

- If the dose in the clinic will be within 6 hours of the subject's scheduled morning dose, the subject should withhold their morning dose of TC, TEZ/IVA, or placebo and the morning dose will be administered in the clinic.
 - If the dose in the clinic will be more than 6 hours after the subject's scheduled morning dose, the subject should take the morning dose of TC, TEZ/IVA, or placebo at home.
6. Subjects will be instructed to bring all used and unused materials associated with the study drug to the site; study drug will be dispensed at each visit, as appropriate.

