12.3 Statistical Analysis

12.3.1 General Considerations

Continuous variables will be summarized using the following descriptive summary statistics: the number of subjects (n), mean, SD, median, minimum value (min), and maximum value (max). The precision of the measurement for each continuous variable will be specified in the SAP. Unless otherwise specified, min and max values will be reported with the same precision as the units of the raw data. The mean, median, and SD will be reported to 1 additional decimal place. Any values that require a transformation to standard units (metric or SI) will be converted with the appropriate precision.

Categorical variables will be summarized using counts and percentages. Percentages will be presented to 1 decimal place.

The **baseline value**, unless otherwise specified, will be defined as the most recent non-missing measurement (scheduled or unscheduled) collected before the first dose of study drug in the Treatment Period (i.e., the Day 1 Visit). For ECG, baseline will be defined as the most recent pretreatment measurement (or the average of triplicate measurements, if the most recent pretreatment measurement is obtained in triplicate) before the first dose of study drug in the Treatment Period (i.e., the Day 1 Visit).

Absolute change from baseline will be calculated as post-baseline value – baseline value.

The **Treatment-emergent (TE) Period for the Run-in Period** will be from the first dose of study drug in the Run-in Period to (1) the first dose of study drug in the Treatment Period for subjects who complete the Run-in Period and continue to the Treatment Period, or (2) 28 days after the last dose date of study drug in the Run-in Period for subjects who do not continue to the Treatment Period (e.g., subjects who do not meet the conditions to enter the Treatment Period).

The **TE Period for the Treatment Period** will include the time from the first dose date of study drug in the Treatment Period (TC or placebo + TEZ/IVA) to 28 days after the last dose of the study drug or to the completion of study participation date (as defined in [Section 9.1.7](#)), whichever occurs first.

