## 12 LIST OF APPENDICES

### Appendix A: Analysis Visit Windows for Safety and Efficacy Assessment

**Table 12-1 Analysis Visit Windows for Safety and Efficacy Assessments**

Assessment	Visit 	Target Study Day	Analysis Visit Window  (in study days)
Safety Assessment			
Serum Chemistry Hematology Standard 12-lead ECG	Day 1 (Baseline)	1	≤1 Pre-dose
	Day 15	15	[1, 22]
	Week 4	29	(22, 43]
	Safety Follow-up	Not applicable	Use nominal visit
Coagulation	Day 1 (Baseline)	1	≤1 Pre-dose
	Week 4	29	[1, 43]
	Safety Follow-up	Not applicable	Use nominal visit
Vital Signs	Day 1 (Baseline)	1	≤1
	Day 15	15	[1,22]
	Week 4	29	(22, 43]
	Safety Follow-up	Not applicable	Use nominal visit
Efficacy Assessment and Pharmacodynamic Assessment			
Spirometry	Day 1 (Baseline)	1	≤1 Pre-dose
	Day 15	15	(1,22]
	Week 4	29	(22, 43]
	Safety Follow-up	Not applicable	>43
Sweat Chloride	Day 1 (Baseline)	1	≤1 Pre-dose
	Day 15	15	(1,22]
	Week 4	29	(22, 43]
CFQ-R Weight, Height and BMI	Day 1 (Baseline)	1	≤1
	Day 15	15	(1,22]
	Week 4	29	(22, 43]
	Safety Follow-up	Not applicable	>43

Notes:

 Visit name for analysis purpose is used to report data in tables and figures.

 The analysis visit windows will be applied using the following rules for both scheduled and unscheduled visits:

- a. If no numerical measurement is available within a visit window, the measurement will be considered missing for the visit.
- b. If there is more than 1 numerical measurement available within a visit window, use the following rules:
  - i. The measurement closest to the target day will be used; or
  - ii. If there are multiple measurements with the same distance from the target day, the latest measurement will be used.

 For lab, ECG and vital sign measurement collected on the date of first dose of study drug in Treatment Period, if it cannot be determined whether the measurement is before or after the first dose:

- a. Scheduled measurement will be treated as pre-dose observation.
- b. Unscheduled measurement will be treated as post-dose observation.

 For safety assessment, Safety Follow-up analysis visit will be based on nominal Safety Follow-up visit. If a subject

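### Does the plan need an earliest date for the CFQ-R baseline, so that a Screening score from before the TEZ/IVA run-in cannot serve?

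*SAP*

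**What the plan says.** SAP 9.1 (General Considerations) states that baseline "is defined as the most recent non-missing measurement (scheduled or unscheduled) collected before the first dose of study drug in the Treatment Period". Protocol 12.3.1 has the same rule: it "will be defined as the most recent non-missing measurement (scheduled or unscheduled) collected before the first dose of study drug in the Treatment Period". In SAP Appendix A, Table 12-1, the row "CFQ-R Weight, Height and BMI" gives the baseline window as study day 1 or earlier, with no lower limit. Unscheduled values also count, since SAP 9.1 uses them "In the derivation of baseline and last on-treatment measurements".

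Protocol Table 3-1 schedules CFQ-R at Screening (Day -56 to Day -29). In Table 3-2 it is blank at Day -28 and Day -14 and next appears at Day 1. Spirometry and sweat chloride, by contrast, are both measured at Day -14. Under SAP 9.3.2.1, a domain with more than half of its items missing gets no score, so a form that was handed in can still be unusable.

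Protocol 9.1.2 says that the run-in is "designed to establish a reliable on-treatment (TEZ/IVA) baseline for the Treatment Period".

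Two provisions protect the Day 1 form. Footnote e of Table 3-2 says that CFQ-R "must be completed before any other assessments scheduled at relevant visits". Protocol 9.6.1 says that the morning dose on visit days "will be administered at the site after predose assessments have been completed".

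**The concern.** The run-in is there so that change is measured from a value taken on TEZ/IVA. Of the three tested endpoints, CFQ-R alone has no scheduled on-run-in value to fall back on. If the Day 1 score is lacking, the rule goes back to a Screening score that is 29 to 56 days old at Day 1, or up to 70 days old with the two-week extension in Protocol 9.1.1.3 (56 + 14).

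Protocol 9.3.1 says that some subjects may be on no CFTR modulator at Screening. For them, the reported change would combine the run-in effect of TEZ/IVA with the change during the Treatment Period. The CFQ-R model in SAP 9.3.2.2 adjusts for baseline ppFEV1 and not for baseline CFQ-R, so it does not correct this.

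The outputs exposed are the baseline CFQ-R summary (SAP 9.2.2) and, in SAP 9.3.2.2, the within-arm LS means with confidence intervals, their plot, and the descriptive summaries of change. If the tested arm difference were exposed too, a key secondary endpoint would be in doubt.

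**Working it through.** **Plan's own figure.** The documents give no CFQ-R effect, SD or power. The only power statement is for ppFEV1. With 50 x 0.95 = 47.5 per arm, a difference of 5.0 and SD 7, a two-sided t-test gives 93.1%, which agrees with the stated 93%. This point does not touch it.

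**Inputs.** From the documents: 50 per arm and a 0-100 score. Assumed, because the documents are silent:
- share of an arm without a scorable Day 1 form, p = 2% to 10% (1 to 5 of 50);
- mean run-in shift in the score, d = 0 to 8 points;
- SD of CFQ-R change, s = 12 to 20.

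Subjects already on TEZ/IVA at Screening would show little or no shift. Setting their number to zero gives the largest effect.

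**Within-arm mean change.** Shift = p x d.

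| p | d = 2 | d = 5 | d = 8 |
|---|---|---|---|
| 2% | 0.04 | 0.10 | 0.16 |
| 5% | 0.10 | 0.25 | 0.40 |
| 10% | 0.20 | 0.50 | 0.80 |

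The within-arm SE is s/sqrt(50): 12/7.07 = 1.70 to 20/7.07 = 2.83. The largest shift is 0.80/1.70 = 0.47 SE. At p = 2% it is 0.16/1.70 = 0.09 SE.

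**Arm difference.** Expected shift = (p in the triple-combination arm - p in the TEZ/IVA arm) x d. Treatment is blinded and the Day 1 form precedes the first randomized dose, so p can differ between arms only by chance and the expectation is zero. The SD of that chance error is d x sqrt(2p(1-p)/50). At p = 10% and d = 8 it is 8 x sqrt(0.18/50) = 0.48 points. The SE of the difference itself is at least 12 x sqrt(2/50) = 2.40.

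A simulation with 50 per arm, a true effect of 10, d = 5 and p = 10% gave within-arm changes of 0.51 and 10.48, where about 0 and 10 are correct. The difference was 9.98.

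**Keeping the fallback against dropping the subjects.** For a constant shift, keeping them multiplies the SE by sqrt(1 + p(1-p)d²/s²). Dropping them multiplies it by sqrt(1/(1-p)). With d = 8 and s = 12, the least favourable case for keeping:

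| p | Keep | Drop |
|---|---|---|
| 2% | +0.43% | +1.02% |
| 5% | +1.05% | +2.60% |
| 10% | +1.98% | +5.41% |

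The older score need not add further variance. If visit-to-visit error is independent and equal across visits, Week 4 minus Screening has the same variance as Week 4 minus Day 1. True differences between subjects in their run-in response would add some.

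**The case for a change.** The best case for acting is that the remedy is nearly free. One could count, by arm, the subjects whose CFQ-R baseline predates their run-in and, if there are any, rerun the model without them. Settling this before database lock would avoid a later choice made with the data in view. The visible SAP plans no such count, and the fallback does run against the stated purpose of the run-in.

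The reading of the rule stands: no CFQ-R-specific provision in the visible text overrides it. The case for a change is weaker:

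- The suggested remedy leaves the baseline rule, the Full Analysis Set and the tested model as they are. It adds a descriptive table and changes no conclusion.
- Subject listings are planned (SAP 8.1 and 9.1), so affected subjects can be found. Parts of the efficacy section are also redacted, so the absence of a count cannot be asserted for the whole SAP.
- The direction of the shift is not known. Protocol 9.5 lets subjects stay on approved or investigational modulators from the same sponsor until Day -28 without washout, so for some the run-in change could be nil or negative.
- Subjects with no validated translation never complete the form (Protocol 11.6.2). They have no Screening score and do not add to the number affected.

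**Conclusion.** No change is needed. The rule is a fair trade-off, stated alike in both documents: it keeps subjects in the analysis at the price of an occasional pre-run-in baseline. The hierarchical CFQ-R test has an expected error of zero, and the chance error has an SD of at most 0.48 points under the assumed ranges. The descriptive within-arm change moves by 0 to 0.8 points, at most 0.47 of its SE. The upper end needs 10% of Day 1 forms to be unscorable, an 8-point run-in gain, and nobody already on TEZ/IVA at Screening. That is hard to square with a questionnaire completed first, at a visit where dosing follows on site.

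These sizes rest on the assumed missing rate, shift and SD. The lack of bias in the arm difference rests on blinding and on the Day 1 form preceding the randomized dose. If the listings showed many pre-run-in baselines, the within-arm CFQ-R changes should be read with that in mind. The comparison between arms would still hold.
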